## **HYPOTHESIS AND OBJECTIVES**

As Null Hypothesis (H0) the investigator assumes that marginal bone loss is similar in all implants, regardless of the type of restoration performed.

The Alternative Hypothesis (H1) is that marginal bone loss does depend on the type of restoration performed.

Formulated the hypothesis, the investigator states the objectives that we have set:

1.- Clinical monitoring of marginal bone loss in various types of prostheses on implants on a sample of patients at one and six months after placement.

2.- Clinical follow-up of other mechanical and biological complications that may occur on these unitary implants.

## **MATERIAL AND METHOD**

Initially, a referal review is carried out based on a bibliographic search through various Medline EMBASE, COCHRANE databases, to locate the state of scientific knowledge at this time on the subject to be investigated.

The keywords used are:

Removal torque, Mechanical complications, Abutment screw, Screw loosening, Cyclic loading, Preload, Technical complications, Abutment angulation, Prosthetic screw, Untightening torque, Biological complications, Survival

This study will analyze the mechanical and biological complications of single implant prostheses. A controlled and randomized clinical trial will be carried out in unitary prostheses. Screw-retained prostheses will be compared on unitary implants subdivided into three groups:

- 1. Prosthesis on interface (unit) + CAD/CAM structure.**
- 2. Direct implant prosthesis + Cad/CAM.**
- 3. Direct prosthesis to implant overcasting techniques.**

The assignment of groups will be carried out using a randomized table of numbers.

**Main variable:** Marginal bone loss.

As secondary variables the investigator will analyze: Implant and prosthesis survival, prosthetic complications, soft tissue stability, type of antagonist, crown height space (the distance between the marginal bone crest and the occlusal plane), demographic variables, social habits (smoking , alcohol).

**Sample size** according to the article by Galindo Moreno 2015:" We are planning a study of a marginal bone loss from independent control (prosthesis direct to implant) and experimental (prosthesis on interface) subjects with 1 control(s) per experimental subject. In a previous study (Galindo-Moreno) the response within each subject group has a true difference in the experimental and control means of 0.77. Considering a normal distribution with a standard deviation of 0.77. If , we will need to study 17 experimental subjects and 17 control subjects to be able to reject the null hypothesis that the population means of the experimental and control groups are equal with probability (power) 0.8. The Type I error probability associated with this test of this null hypothesis is 0.05.

Therefore, we need 17 implants \* 3 groups \* 15% "drop outs" this leads to a sample size of 59 implants.

We will study their biological complications by means of a radiographic study of the crestal bone loss at 0, 3 and 6 months after prosthodontic rehabilitation. For this, we will protocolize the taking of periapical radiography using the parallelism technique and an invariable personalized positioner.

The loads on the different elements of the implant-prosthetic system will be studied using the finite element technique: crown-connection screw, intermediate abutment interface, if used, and intermediate abutment-implant.

The adjustment between the CAD/CAM structures and the intermediate abutments with or without interface will also be studied using electron microscopy.

A prospective clinical study will be carried out at 3 and 6 months, extendable up to a year, in patients recruited in the Léon Master of Surgery in whom BTI unitary implants have been placed in any location, with a universal platform. The informed consent of the patient will be previously obtained in order to be included in the study, also complying with the agreement reached with the ethics committee for the same. In this trial, the prosthesis will be loaded, dividing the cases into the previously described subgroups.

The CAD/CAM part will be carried out at the BTI Institute, with the porcelain being loaded at the Carretero Dental laboratory.

We will analyze the changes produced in this period of time on the soft tissues, scanning them with an intraoral scanner, being able to make the comparison at 0, 3 and 6 months. Likewise, among the possible mechanical complications that may occur, chipping, fractures, debonding or loosening of the screw will be studied. We will analyze the latter by digital ratchet.

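### Does the protocol treat baseline characteristics as outcomes, and does crown height space contaminate the bone-loss comparison?

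*Protocol*

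**What the plan says.** Material and Method names one main variable, "Marginal bone loss". The next sentence opens the list of secondary variables: "As secondary variables the investigator will analyze: Implant and prosthesis survival, prosthetic complications". The same sentence continues with "soft tissue stability, type of antagonist, crown height space (the distance between the marginal bone crest and the occlusal plane), demographic variables, social habits", the habits being smoking and alcohol. The protocol does not divide the list. It does not say which entries are outcomes, covariates or descriptors.

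Crown height space is defined as "the distance between the marginal bone crest and the occlusal plane", with no measurement time. Bone loss does have a schedule: "radiographic study of the crestal bone loss at 0, 3 and 6 months after prosthodontic rehabilitation". Soft-tissue scans are planned at the same three times. Patients are those "in whom BTI unitary implants have been placed in any location", and groups are assigned from a table of random numbers.

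The section Hypothesis and Objectives gives two aims: to follow marginal bone loss across prosthesis types, and to follow other mechanical and biological complications.

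**The concern.** Two things catch the eye.

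First, the list mixes two kinds of variable. Survival, prosthetic complications and soft-tissue stability can be effects of the restoration. Antagonist type, demographics, smoking and alcohol describe the patient or site and are not plausible effects of it. Because the list follows directly after the main variable and says the investigator will analyse its entries, it can be read as a list of secondary endpoints. Testing such characteristics between randomised groups as results would tell the reader only about chance. On that reading, useful prognostic data would also be kept out of the bone-loss model in a small trial with implants in any location.

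Second, crown height space starts at the marginal bone crest, the landmark whose movement is the main variable. If the occlusal plane stays fixed, every unit of bone loss adds one unit to a later crown height space. Reporting a follow-up value as an outcome would partly repeat the main result. Adjusting for it would remove part of the effect under study.

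**Working it through.** **1. The plan's own figure.** Inputs from the sample-size paragraph: difference 0.77, SD 0.77, type I error 0.05 (taken as two-sided), power 0.8. The standardised difference is 0.77 / 0.77 = 1. The two-sample t-test then needs 16.71 per group, so 17, as stated. At 17 per group the noncentrality is 1 × √(17/2) = 2.92 and the degrees of freedom are 32, which gives power 0.807. For three groups, 17 × 3 = 51 and 51 × 1.15 = 58.65, so 59, also as stated. None of these figures uses a covariate or depends on how the secondary list is read.

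**2. What adjustment could add.** If covariates explain a share R² of the variance, the standardised difference becomes 1 / √(1 − R²) and the standard error shrinks by the factor √(1 − R²). With error pooled over three groups and three covariate degrees of freedom, df = 51 − 3 − 3 = 45. Every R² is an assumption.

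| Assumed R² | SE factor | Power |
|---|---|---|
| no adjustment, pooled, df 48 | 1 | 0.815 |
| 0.02 | 0.990 | 0.822 |
| 0.05 | 0.975 | 0.833 |
| 0.1 | 0.949 | 0.852 |
| 0.2 | 0.894 | 0.891 |
| 0.3 | 0.837 | 0.926 |

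The like-for-like starting point is 0.815, because 0.807 rests on two-group degrees of freedom. The unadjusted comparison already exceeds 0.8, so the table shows a possible gain in efficiency and no shortfall.

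**3. How crown height space could matter.** Suppose it were measured at 6 months with the occlusal plane fixed. It would then equal the month-0 value plus bone loss. Let the month-0 value have SD s, be independent of bone loss, and be in the same unit as 0.77. The built-in correlation is r = 0.77 / √(0.77² + s²). Adjusting for the 6-month value alone would multiply the group difference by 1 − r². Every s is an assumption.

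| Assumed s | r | Share of difference removed (r²) | 0.77 would appear as |
|---|---|---|---|
| 1 | 0.61 | 37% | 0.48 |
| 1.5 | 0.46 | 21% | 0.61 |
| 2 | 0.36 | 13% | 0.67 |
| 3 | 0.25 | 6% | 0.72 |

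This harm needs two conditions together: a post-loading measurement, and its use as a covariate. If the value is taken at month 0, the built-in coupling does not arise and crown height space is a legitimate baseline covariate.

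**4. Whether the protocol meets those conditions.** It schedules serial measurement of bone loss and of soft tissues, and gives crown height space no such schedule. It names no model that adjusts for crown height space at any time. It specifies no test between groups of smoking, alcohol, demographics or antagonist type, and neither objective mentions them.

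**The case for a change.** The strongest case for the concern is that defining secondary outcomes is the protocol's job, not something to leave to the analysis plan. The list sits beside the main variable and says that its entries will be analysed, so reading it as a list of endpoints is natural. A crown height space without a measurement time leaves a damaging use open, with up to 37% of the effect lost under the smallest SD assumed above. At 17 implants per group, chance imbalance in something like smoking is also quite possible.

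Part of this stands. The list would be clearer if split, and a measurement time for crown height space would remove a doubt. The arithmetic behind the possible harm and the possible gain is correct.

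The rest does not carry. Variable is a broad word that covers explanatory and descriptive data, and a list that includes demographics and habits is most naturally a list of what will be recorded and examined. Leaving a misuse open is not the same as planning it. Chance imbalance does not bias a randomised comparison; its type I error already allows for such imbalance. Choosing a model and its covariates commonly belongs to the statistical analysis plan, and nothing in the protocol rules out using these data as covariates there.

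**Conclusion.** The concern does not hold. The protocol does not call these characteristics outcomes, plans no test of them between groups, and neither measures crown height space serially nor adjusts for a follow-up value. The primary comparison is valid without adjustment and reaches power 0.807 at 17 per group on the protocol's own difference and SD, with a two-sided 0.05 test. Sample size and type I error are untouched. The gains to 0.852, 0.891 and 0.926 rest wholly on assumed R² values, and the attenuation of 6% to 37% rests on assumed SDs and on a use that the protocol never states. What remains is an undivided list and an unstated measurement time, which is missing detail and not an error in the plan.

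### Single implants at any site are eligible, but the allocation names no location factor and location is not among the variables to be analysed: an avoidable loss of precision and credibility, not of validity

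*Protocol*

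**What the plan says.** All the relevant text is under Material and Method in the protocol.

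- **Eligibility.** The prospective clinical study takes patients "in whom BTI unitary implants have been placed in any location, with a universal platform". No restriction by jaw or tooth position is stated.
- **Allocation.** "The assignment of groups will be carried out using a randomized table of numbers". No stratum, block or other balancing device is mentioned.
- **Main variable.** "Marginal bone loss".
- **Secondary variables to be analysed.** "Implant and prosthesis survival, prosthetic complications, soft tissue stability", and then "type of antagonist, crown height space (the distance between the marginal bone crest and the occlusal plane), demographic variables, social habits", with smoking and alcohol given as the habits. Jaw, tooth position and implant location do not appear.
- **Imaging.** For crestal bone, "we will protocolize the taking of periapical radiography using the parallelism technique and an invariable personalized positioner", at 0, 3 and 6 months.
- **Sample size.** A "true difference in the experimental and control means of 0.77", a standard deviation of 0.77, type I error 0.05 and power 0.8 give 17 per group. Three groups and 15% drop-outs bring this to 59 implants.

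**The concern.** The protocol opens eligibility on one feature of the implant, its site, and then neither balances that feature nor names it for analysis. It does name two other local features, antagonist and crown height space, so the investigators evidently regard local conditions as relevant.

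Groups of 17 are small enough for plain chance to leave a visible difference in site mix between restorations. If bone loss varies by site, two things follow. Site variation stays in the error term of the only hypothesis the trial tests. And a reader who sees an uneven site mix beside a borderline result will doubt it. An adjustment added after the imbalance has been seen is less convincing than one named in advance.

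**Working it through.** **1. The plan's own figures.** Inputs from the sample size paragraph: difference 0.77, SD 0.77, alpha 0.05, power 0.8. The test is taken as two-sided because the alternative hypothesis has no direction.

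- Standardised difference: 0.77 / 0.77 = 1.0.
- Two-sample t-test: n = 16.7, rounded up to 17 per group. Power at 17 is 0.807.
- Total: 17 × 3 = 51, and 51 × 1.15 = 58.65, rounded up to 59.

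Both stated figures reproduce. 59 / 3 is about 20 implants allocated per group.

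**2. How often chance leaves the groups uneven.** Assumption: each implant falls in one of two location classes with probability p, independently in each group. The protocol gives no location mix, so p = 0.5 is used, with 0.3 and 0.7 as a range. Counts are Binomial(n, p). The third column is the probability for one given pair of groups. The last is the probability that the largest of the three pairwise gaps reaches the stated size.

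| n per group, gap | p | one given pair | at least one of three pairs |
|---|---|---|---|
| 17, 4 or more (at least 4/17 = 23.5 points) | 0.5 | 0.23 | 0.45 |
| 17, 4 or more | 0.3 or 0.7 | 0.19 | 0.39 |
| 20, 4 or more (at least 20 points) | 0.5 | 0.27 | 0.51 |
| 20, 5 or more (at least 25 points) | 0.5 | 0.15 | 0.33 |

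**3. How far such a gap moves the result.** Let R² be the share of the planning variance explained by a two-class location factor split 50/50. A location effect g contributes variance g²/4, so g = 2 × 0.77 × √R². A 4-of-17 gap shifts the difference between two groups by g × 4/17.

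| R² (assumed) | g | shift |
|---|---|---|
| 0.05 | 0.34 | 0.08 |
| 0.10 | 0.49 | 0.11 |
| 0.20 | 0.69 | 0.16 |

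The standard error of a two-group difference is 0.77 × √(2/17) = 0.26. Each shift is smaller than that, and all are well below the planned 0.77.

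**4. What including location would gain.** With location in the model the residual SD is 0.77 × √(1 − R²), so the standardised difference becomes 1/√(1 − R²). Two-sided t-test, 17 per group:

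| R² (assumed) | standardised difference | power, 32 df | power, 31 df (one spent on location) |
|---|---|---|---|
| 0 | 1.000 | 0.807 | 0.806 |
| 0.05 | 1.026 | 0.826 | 0.826 |
| 0.10 | 1.054 | 0.846 | 0.845 |
| 0.20 | 1.118 | 0.885 | 0.884 |

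The gain is about 2 to 8 percentage points of power. The lost degree of freedom costs less than 0.1 of a point. The calculation takes the planning SD of 0.77 to include site variation, which the protocol does not say.

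**The case against.** A reader might infer that a location imbalance can be neither prevented nor corrected, and that its effect would be taken for an effect of the restoration. The protocol does not support that. Each implant's site is known to the clinic and can be read from its periapical radiographs, so location can be tabulated and adjusted for even though it is not listed. The list is of variables to be analysed, not a complete data-collection form. Randomisation keeps the comparison unbiased on average, and the type I error already allows for chance imbalance in any factor, measured or not.

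Three further points have force.

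- Covariate choice is commonly left to a statistical analysis plan, and that plan is not at hand.
- The protocol gives neither a location mix nor a location effect on bone loss, so every figure for the size of the problem rests on assumption. On those assumptions the shift stays below one standard error, and the planned power already meets its 0.80 target.
- Admitting every site is a legitimate choice, and no statement in the protocol contradicts another on this matter.

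All of this stands, and it limits the point to precision and credibility. It does not dispose of it. A later analysis plan can add a covariate, but it cannot stratify a list that has already been used. Allocation is a protocol matter, and this protocol settles it with a plain number table. Nor does counting allocated rather than evaluable implants remove the imbalance: at 20 per group, a gap of 5 or more still arises in some pair with probability 0.33.

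It is also tempting to object that the time from implant placement to loading is not listed. Nothing in the protocol shows that this interval matters to the comparison, so that would only be a request for more detail.

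**Conclusion.** The point holds as a design improvement. Eligibility covers every site, no location factor is stated for the allocation, and location is not named for analysis. With an assumed even split between jaws, the probability that some pair of groups differs by 4 or more of 17 implants is about 0.45 (0.39 if the split is 30/70). If location explains an assumed 5-20% of the variance, the planned comparison forgoes a rise in power from 0.807 to about 0.83-0.88. Should location have no effect on bone loss, there is no gain in power, and the benefit is limited to groups that are visibly alike.

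This is neither a numerical error nor a threat to validity: 17 per group and 59 implants stand.

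**What to change.** In the protocol, before allocation begins:

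1. Add implant location (jaw, and anterior or posterior) to the recorded variables.
2. Prepare the random list in two strata by one prespecified location factor, for example upper or lower jaw, using small permuted blocks across the three groups.
3. State that this factor will be included in the comparison of marginal bone loss.

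Keep eligibility open to all sites, and keep the sample size.

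The cost is one line in the variable list and two lists instead of one, with no extra patients, visits or procedures. The downsides are one degree of freedom in the model and slightly incomplete blocks at the end of each stratum. Any location feature not used as the stratum, such as front versus back if jaw is chosen, remains balanced only by chance. If allocation has already started, the first and third steps can still be taken, provided the covariate is fixed before the bone-loss data are examined by group.

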#### **AVAILABLE MEANS TO CARRY OUT THE PROJECT:**

The facilities of the solidarity clinic will be used, where the clinical and theoretical practices of the Master's Degree in Surgery, Periodontics and Implantology of the University of León ([name]) are carried out.

The BTI implant house will provide us with the transepithelial and CAD/CAM structures as well as the facilities and technologies necessary for the study of finite elements and electron microscopy.

#### **APPLICABILITY AND PRACTICAL USE:**

Implants are increasingly used in daily practice. Their long-term survival and prognosis depend largely on the type of restoration carried out on them. We must analyze the design parameters of our restorations that can influence the appearance or not of biological or mechanical complications on our implants, in order to be able to transfer this information to the decisions that we must carry out in our clinical practice as dentists.

